**Statistical Analysis Plan**

Sponsor: Selecta Biosciences

Protocol No.: SEL-212/302

- Physical Role Functioning
- Emotional Role Functioning
- Social Role Functioning
- Mental Health

**9.3.2.4. *In patients with tophi at Baseline, the percentage of patients with at least PR (as best response) in overall tophus response evaluation until Day 28 of Treatment Period TP6***

This efficacy endpoint considers the patients with tophi at baseline and compares between each SEL-212 and placebo the percentage of patients with at least PR (as best response) in the overall tophus response evaluation until Day 28 of TP6. The statistical testing of each SEL-212 treatment group versus placebo in both estimands, as well as the estimands where the ITT is replaced by each mITT, all randomized and PP sets, of this key secondary efficacy will be performed using the Chi-square test with continuity correction with a two-sided type 1 error rate  $\alpha = 2.5\%$  to adjust for the two comparisons against placebo. In the main estimand, patients with missing information on tophus response until Day 28 of TP6 will be multiple imputed using the logistic method considering the treatment group.

Frequency table of tophaceous patients at baseline with best response in the overall tophus evaluation resulting in at least PR / stable disease progressive disease will be provided by treatment group and period on the ITT, the defined mITT populations, all randomized and the PP population.

The time until the first tophus reduction (i.e. the first time CR or PR is assessed in overall tophus response) will be summarized using descriptive statistics by treatment group for tophaceous patients at baseline in the ITT, the defined mITT populations, all randomized and the PP population. Tophus photography can be repeated on TP1D0 or until 14 days post TP1D0 if initial images submitted to the Central Reader were not collected per acquisition guidelines.

**9.3.2.5. *Percentage of patients who achieve and maintain reduction of sUA < 6 mg/dL for at least 80% of the time during Treatment Period TP6 in subset of patients with tophi at baseline***

Both estimands, as well as the estimands where the ITT is replaced by each mITT, all randomized and PP sets, for this key secondary endpoint will be analysed in the same way as the primary endpoint, except a Chi-square test with continuity correction will be performed, given only patients with tophus at baseline will be included in the analysis. In addition, the logistic model used to carry out multiple imputation for missing response evaluation data in TP6 will only include the treatment group in the model (and not tophus status at baseline), as only patients with tophus at baseline will be included in the analysis.

**9.3.2.6. *The change from Baseline to Day 28 of Treatment Period 6 in number of tender joints***

Both estimands, as well as the estimands where the ITT is replaced by each mITT, all randomized and PP sets, for this key secondary efficacy will be tested between each SEL-212 treatment group versus placebo using the mixed model for repeated measures (MMRM) with change in tender joints from baseline as dependent variable and treatment, period, treatment-by-period interaction, randomization stratum and baseline value of tender joints as fixed effect variables. The unstructured covariance structure will be used for the MMRM. The Least Square (LS) Mean difference between each SEL-212 and placebo treatments groups will be estimated on the treatment-by-visit interaction at TP6-Day 28 visit, along with its 97.5% confidence interval, and 2-sided p-values.

This document is confidential.

SAP Version: 1.1, 22 Feb 2023

Filing requirements: TMF

**Statistical Analysis Plan**  
 Sponsor: Selecta Biosciences  
 Protocol No.: SEL-212/302

---

A sensitivity analysis will be performed for the main estimand: missing values of number of tender joints at Day 28 TP6 will be multiple imputed by using the regression and predictive mean matching (RPMM) method considering tophus status at baseline and treatment group. The change from baseline to Day 28 of TP6 in tender joints will be analyzed using an ANCOVA with treatment and randomization stratum as fixed effects and the baseline value of tender joints as covariate.

The number of tender joints at scheduled visits and the change from baseline will be summarized by treatment group and period on the ITT, the defined mITT populations, all randomized and the PP population.

**9.3.2.7. *The change from Baseline to Day 28 of Treatment Period 6 in the total score of the Health Assessment Questionnaire***

Both estimands, as well as the estimands where the ITT is replaced by each mITT, all randomized and PP sets, for this key secondary efficacy will be tested between each SEL-212 treatment group versus placebo using MMRM with change in HAQ-DI total score as dependent variable and treatment, period, treatment-by-period interaction, randomization stratum and baseline value of HAQ-DI total score as fixed effect variables. The unstructured covariance structure will be used for the MMRM. LSMean difference between each SEL-212 and placebo treatments groups will be estimated on the treatment-by-visit interaction at TP6-Day 28 visit, along with its 97.5% confidence interval, and 2-sided p-values.

A sensitivity analysis will be performed for the main estimand: missing values of HAQ-DI total score at TP6-Day 28 will be multiple imputed by using the RPMM method considering tophus status at baseline and treatment group, and the change from baseline to Day 28 of TP6 in HAQ-DI total score will be analyzed using an ANCOVA with treatment and randomization stratum as fixed effects and the baseline value of HAQ-DI total score as covariate.

The HAQ-DI total score at scheduled visits and the change from baseline will be summarized by treatment group and period on the ITT, the defined mITT populations, all randomized and the PP population.

The HAQ-DI, which includes the patient global assessment and pain scale, is an instrument that assesses fine movements of the upper extremity, locomotor activities of the lower extremity, and activities that involve both the upper and lower extremities. Standard scoring takes into account the use of aids and devices or assistance from another person. There are 20 items in 8 categories that represent a comprehensive set of functional activities: dressing, rising, eating, walking, hygiene, reach, grip, and usual activities. The stem of each item assesses a patient's functional ability using their usual equipment during the past week. Each category contains at least 2 specific sub-category questions. For example, under the category "walking," patients are asked about their ability to walk outdoors on flat ground and to climb up 5 steps.

The HAQ-DI includes a patient global assessment of disease and a visual analog scale for pain assessment.

Eight (8) categories will be assessed by the HAQ-DI: 1) dressing and grooming, 2) arising, 3) eating, 4) walking, 5) hygiene, 6) reaching, 7) gripping, and 8) common daily activities. There are 2 or 3 questions for each section. Scoring within each section is on a 4-point Likert scale from 0 (without any difficulty) to 3 (unable to do). The score given to each section is the worst (highest) score within the section (ie, if one question is scored 1 and another 2, then the score for the section is 2). In addition, if an aid or device is used or if help is required from another individual, then the minimum score for that section is 2. If the section score is already 2 or more then no modification is made. The sum of the 8 scores of the 8 sections will be divided by 8 to obtain the HAQ-DI total score. In the event that one section is not

This document is confidential.

**Statistical Analysis Plan**

Sponsor: Selecta Biosciences

Protocol No.: SEL-212/302

completed by a patient then the summed score would be divided by 7. The HAQ-DI total score will be calculated if 6 or more sections are available, otherwise it will be defined at missing.

### **9.3.2.8. Gout Flare Incidence During Treatment Periods 1-6**

The gout flare incidence is defined as the total number of gout flares a patient experiences in respective time period divided by the length of observation of the patient in this time period. Both estimands, as well as the estimands where the ITT is replaced by each mITT, all randomized and PP sets for this key secondary efficacy will be tested between each SEL-212 treatment group versus placebo using ANOVA model with incidence of gout flares as dependent variable and treatment and randomization stratum as fixed effect variables. Missing values of gout flare incidence by TP6-Day 28 will be multiple imputed by using the RPMM method considering tophus status at baseline and treatment group. The LSMean difference between each SEL-212 and placebo treatments groups will be provided along with its 97.5% confidence interval, and 2-sided p-values.

In a supportive analysis, for each defined estimand the comparison between each SEL-212 treatment group and placebo will be performed using MMRM with the dependent variable 'incidence of gout flares in the study (TP1-6)' and treatment, 3-month period (months 1-3 versus months 4-6), treatment-by-3-month period interaction and randomization stratum as fixed effects. The LSMean difference between each SEL-212 and placebo treatment groups will be presented for each 3-month period, along with its 97.5% confidence interval, and 2-sided p-values.

In a further supportive analysis, the total number of gout flares by TP6-Day 28 will be analyzed. Missing values of total number of gout flares by TP6-Day 28 will be multiple imputed by using the RPMM method considering tophus status at baseline and treatment group. The total number of gout flares will be analyzed using an ANOVA with treatment and randomization stratum as fixed effects.

A summary table of the incidence of gout flares during the study and stratified by 3 months period (month 1-3 and month 4-6 after start of study treatment) will be provided by treatment group on the ITT, mITT, all randomized and PP populations. Summary tables of the total number of gout flares during the study will be provided by treatment group in overall and additionally stratified by severity on the ITT, mITT and PP populations. Summary tables of the number of gout flares during the first 3 months (TP1-3) and the next three months (TP4-6) will be provided by treatment group in overall and additionally stratified by severity on the ITT, mITT, all randomized and PP populations.

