5.4 Impact on Quality of Life

One longitudinal study in this patient population reports that approximately 70% of patients with chronic refractory gout have at least 1 tophus and an average of 7 flares per year. In a separate study of chronic refractory gout, patients self-reported more than 60% of these flares as crippling ([Brook 2010](#)). Symptoms of pain, limited mobility, and disability are debilitating and deeply affect physical function and emotional and social functioning, and disease severity correlates with a marked compromise in quality of life ([Strand 2012](#), [Becker 2009](#)).

The relationship between self-reported quality of life and disability and disease severity have been evaluated in multiple clinical studies. Over 100 subjects with chronic refractory gout evaluated using the Medical Outcomes Study Short Form-36 assessment, and results revealed that patients with chronic refractory gout have significantly lower subscales analogous to those of 75-year old individuals ([Becker 2009](#)). Specifically, disease severity, as characterized by number of flares in the past year, number of tender or swollen joints, or presence of tophi, significantly correlates with worse quality of life scores in all areas, which include bodily pain, general health, mental health, physical functioning, and vitality. Subjects with comorbidities experienced worse physical functioning ([Strand 2012](#)).

There is also evidence that gout affects workplace productivity, as studies in patients with chronic, refractory gout self-report work absences due to flares, losing 25.1 workdays on average per year.

Another study specifically found employees with gout missed 4.56 more days of work per year than those without gout ([Edwards 2011](#)).

Hospitalizations with a principal diagnosis of gout has steadily increased over the past 2 decades ([Lim 2016](#)). In contrast, hospitalizations due to rheumatoid arthritis (RA) has dramatically decreased over this same time period correlating with the development of effective biologic drugs to treat RA. In 2005, the number of hospitalizations due to gout exceeded the number of hospitalizations due to RA, and this gap has steadily increased. Hospitalization costs for gout and RA show a similar trend. Similarly, general population studies have shown a substantial reduction in premature death in RA patients but not in gout patients ([Rai 2016](#)). The findings likely reflect lack of effective therapies for severe gout.

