### 7.3. Missing Data

Missing data will be imputed for the primary efficacy and key secondary efficacy variables as described in Section 9.

Missing or incomplete dates in safety data: In all listings, missing or incomplete dates will be left as they have been recorded. However, for calculation and sorting based on dates and for consideration in summary tables, the following method will be used: The most conservative approach will be systematically considered (i.e. if the onset date of an AE/concomitant medication is missing or incomplete, it is assumed to have occurred during the study treatment phase (i.e. a TEAE for AEs) except if the partial onset date indicates differently). A missing/incomplete date of medical history or disease diagnosis will be assumed to have occurred before any study treatment.

Missing TEAE relationship will be imputed by 'related' for tabulation.

This document is confidential.

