**Statistical Analysis Plan**  
 Sponsor: Selecta Biosciences  
 Protocol No.: SEL-212/302

---

In a supportive analysis, the total number of gout flares by TP3-Day 28 will be analyzed. Missing values of total number of gout flares by TP3-Day 28 will be multiple imputed by using the RPMM method considering tophus status at baseline and treatment group. The total number of gout flares will be analyzed using an ANOVA with treatment and randomization stratum as fixed effects.

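### The supportive analyses of total gout flare count do not define when an early leaver's total is missing, and both possible readings mishandle these patients

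*SAP*

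**What the plan says.** SAP 9.3.2.8 first sets out the confirmatory flare analysis. It is an ANOVA on incidence, for which that section gives this definition: "total number of gout flares a patient experiences in respective time period divided by the length of observation of the patient in this time period". A supportive MMRM on incidence follows, and then a further supportive analysis of the total count by Day 28 of Treatment Period 6. For that count the SAP says "Missing values of total number of gout flares by TP6-Day 28 will be multiple imputed by using the RPMM method", and the model is the "RPMM method considering tophus status at baseline and treatment group". Then: "The total number of gout flares will be analyzed using an ANOVA with treatment and randomization stratum as fixed effects".

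SAP 9.3.2.9 uses the same scheme for the first three periods: "Missing values of total number of gout flares by TP3-Day 28 will be multiple imputed by using the RPMM method".

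SAP 9.3.2.6 spells out the abbreviation, as the "regression and predictive mean matching (RPMM) method considering tophus status at baseline and treatment group".

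The general rule in SAP 7.3 adds nothing specific to flare counts: "Missing data will be imputed for the primary efficacy and key secondary efficacy variables as described in Section 9". SAP 7.4, on unscheduled visits, does not address partial counts either. No section says when a flare total is missing, makes the recorded count a lower bound, or brings observation time into the count analysis.

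**The concern.** A cumulative count is only partly missing in a patient who leaves early. Protocol 11.2.2 has flares assessed at each visit of the Treatment Phase, so the count up to departure is known and the full-period total cannot be smaller. An imputation that sees only arm and tophus status cannot use that information. Accepting the partial count as the total is no better, because a shorter observation window is then analysed as if it were complete.

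These analyses sit beside key secondary endpoints 8 and 9. A supportive analysis ought to show whether the flare result is robust to how early leavers are handled. This one either sets aside what is known about them or treats their follow-up as complete, and the SAP leaves the programmer to choose.

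**Working it through.** **Inputs**

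- Treatment Phase of 168 days: SAP 3.3.
- Early termination of about 8%, and 47 patients per arm: SAP 3.5. The SAP uses the 8% as 32 / 0.92 = 34.8, rounded up to 35 per arm, which reproduces its figure. Applied to 47 per arm it gives 0.08 x 47 = 3.76, or about 4 patients.
- Background flare rate: Protocol 5.4 cites "an average of 7 flares per year" in chronic refractory gout. It is not a trial assumption and is used here for illustration only.
- Assumed, not in the documents: departure at Day 84; counts that are Poisson or negative binomial with shape 2, 1 or 0.5; and, in one scenario, leavers who flare at twice the average rate.

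The documents give no figure for the flare-count imputation itself, so there is none to reproduce.

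**Expected counts**

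- 168 days: 7 x 168 / 365.25 = 3.22 flares.
- First 84 days: 7 x 84 / 365.25 = 1.61 flares.

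**Reading A: the leaver's total is missing and is imputed**

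Three arms by two tophus levels give at most six predicted means. Predictive mean matching fills in another patient's observed total. The donor may come from a neighbouring cell, but the draw does not depend on the leaver's own flares. The chance that the imputed total falls below the recorded count is the sum over k of P(recorded = k) x P(donor total < k):

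| Count distribution | Leaver at average rate | Leaver at twice average rate |
|---|---|---|
| Poisson | 16% | 42% |
| Negative binomial, shape 2 | 25% | 44% |
| Negative binomial, shape 1 | 28% | 43% |
| Negative binomial, shape 0.5 | 29% | 41% |

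At shape 1 or Poisson, moving an average-rate leaver's departure to Day 28 gives 3% (Poisson) or 11% (shape 1), and to Day 140 gives 33% or 39%. A patient with exactly 4 recorded flares gets a lower total in 60% of draws (Poisson) or 66% (shape 1). Over Treatment Periods 1-3 (mean 1.61), a patient with 3 recorded flares gets a lower total in 78% of draws (Poisson).

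Effect on one arm's mean:

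- Leavers at the average rate: the true and imputed means are both 3.22, so the bias is 0.
- Leavers at twice the average rate: the true mean is 6.44 and the imputed mean 3.22, so the shortfall is 0.08 x (6.44 - 3.22) = 0.26. The arm mean is 3.22 instead of 3.48.

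**Reading B: the partial count is kept as the total**

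Nothing recorded is lost, but the ANOVA has no term for observation time.

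- Leaver at the average rate: 1.61 is analysed in place of an expected 3.22, an arm shortfall of 0.08 x (3.22 - 1.61) = 0.13.
- Leaver at twice the average rate: 3.22 in place of 6.44, an arm shortfall of 0.08 x (6.44 - 3.22) = 0.26.

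**Scale**

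The standard error of a difference between two arms of 47 is the square root of 2 x variance / 47.

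- Poisson (variance 3.22): 0.37.
- Shape 0.5 (variance 3.22 + 3.22^2 / 0.5 = 23.95): 1.01.

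So 0.26 is about 0.3 to 0.7 standard errors, and only if the other arm had no shortfall at all.

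**The case against.** The strongest reply is that the SAP never says an early leaver's total is set to missing. SAP 9.3.2.8 words the imputation of incidence in the same way, and incidence is computable for anyone with some follow-up. If missing means the same in both sentences, no recorded flare is discarded. This stands. A reader might infer that the SAP throws away recorded flares, but the text supports only that it may. It does not rescue the analysis, because the partial count then enters an ANOVA without follow-up time, which is reading B.

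The stakes are also low, and this too stands. The count is a further supportive analysis and only main estimands are confirmatory (SAP 9.3.1). The SAP also plans summaries of incidence and count, the percentage of patients with a flare, diary incidence and, for Periods 1-6, the supportive MMRM. Patients withdrawn from study drug stay in visits to the end of Treatment Period 6 (Protocol 7.1.3), and early termination means withdrawn consent or loss to follow-up (Protocol 8.3.3.1), so few totals are incomplete.

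Finally, an imputed total below the recorded one is a patient-level contradiction, not in itself a bias. With average-rate leavers the imputed arm mean is unbiased. The twice-average rate has no source in the documents, and under equal flare rates and departures the shortfall cancels between arms. The background rate may also be too high for patients on flare prophylaxis (Protocol 10.6.1); lower rates shrink the absolute shortfall. All of this stands and limits the severity.

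**Conclusion.** The point holds as a minor one. SAP 9.3.2.8 and 9.3.2.9 leave undefined when a flare total is missing, and neither reading treats early leavers properly. Under imputation, the total falls below the recorded count in about 16-29% of draws for an average-rate leaver at Day 84, given 7 flares per year and the count distributions above. If the partial count is kept, leavers are undercounted. About 4 of 47 patients per arm are affected.

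Two stronger conclusions might be drawn, and the documents do not support either. One is that the confirmatory flare test is compromised: it divides flares by observed time, so it can use a partial count and is not the subject here. The other is that the treatment difference is biased by 0.26 flares: that figure is one arm's mean under an assumed twice-average leaver rate. The effect on the difference depends on how departures, and the flare rates of those who depart, differ by arm, which the documents do not give.

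**What to change.** In SAP 9.3.2.8 and 9.3.2.9, replace the sentence that imputes the total count, using one of two options:

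1. Keep every recorded flare. Impute only the count in the unobserved time, conditional on the patient's own count and observation time, treatment group and tophus stratum, and add the two. A total below the recorded count is then impossible.
2. Drop the imputation. Analyse observed counts by negative binomial regression with log observation time as offset, and treatment and tophus stratum as factors.

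Either option settles what happens to a partly observed total; the text should say so explicitly. The cost is SAP wording and a small program change. No new data are needed and no confirmatory analysis changes.

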### **9.3.2.9. Gout Flare Incidence During Treatment Periods 1-3**

The gout flare incidence is defined as the total number of gout flares a patient experiences in respective time period divided by the length of observation of the patient in this time period. Both estimands, as well as the estimands where the ITT is replaced by each mITT, all randomized and PP sets, for this key secondary efficacy will be tested between each SEL-212 treatment group versus placebo using ANOVA model with incidence of gout flares as dependent variable and treatment and randomization stratum as fixed effect variables. Missing values of gout flare incidence by TP3-Day 28 will be multiple imputed by using the RPMM method considering tophus status at baseline and treatment group. The LSMean difference between each SEL-212 and placebo treatments groups will be provided along with its 97.5% confidence interval, and 2-sided p-values.

This document is confidential.

